DDI EORTC EORTC/MSG	Drug-drug interaction European Organisation for Research and Treatment of Cancer European Organization for Research and Treatment of Cancer/Invasive Fungal Infections Cooperative Group and the National Institute of Allergy and Infectious Diseases Mycoses Study Group
ESCMID	European Society of Clinical Microbiology and Infectious Diseases
EU	European Union
EudraCT	European drug regulatory affairs Clinical Trials
GCP GVHD HSCT IA	Good Clinical Practice Graft Versus Host Disease Hematopoietic stem cell transplantation Invasive Aspergillosis
IB	Investigator's Brochure
IC ICH iMTA IRB IV	Informed Consent International Conference on Harmonization of Technical Requirements for Registration of Pharmaceuticals for Human Use institute for Medical Technology Assessment Institutional review board Intravenous
IMP	Investigational Medicinal Product
IMPD	Investigational Medicinal Product Dossier
METC	Medical research ethics committee (MREC); in Dutch: medisch ethische toetsing commissie (METC)
MITT MSG PCR	Modified intention to treat Mycoses Study Group Polymerase Chain Reaction
PO QALY	Per os (oral intake) Quality-adjusted life year
RAMS RT	Azole reistance associated mutations Resistance

(S)AE	(Serious) Adverse Event
SOC SOT SPC	Standard of care Solid Organ Transplant Summary of Product Characteristics
Sponsor	The sponsor is the party that commissions the organization or performance of the research, for example a pharmaceutical company, academic hospital, scientific organisation or investigator. A party that provides funding for a study but does not commission it is not regarded as the sponsor but referred to as a subsidizing party.
SUSAR SWAB	Suspected Unexpected Serious Adverse Reaction Stichting Werkgroep Antibioticabeleid (in Dutch)
TR	Tandem Repeat
Wbp	Personal Data Protection Act (in Dutch: Wet Bescherming Persoonsgevens)
WMO	Medical Research Involving Human Subjects Act (in Dutch: Wet Medisch-wetenschappelijk Onderzoek met Mensen

SUMMARY

Rationale

Patients with underlying haematological malignancies or immunocompromised for various other reasons, are prone to fungal infections. Invasive aspergillosis (IA) is a common complication during remission inducing chemotherapy for acute leukemia or other hematological malignancies, as well as those who have undergone allogeneic hematopoietic stem cell transplantation (HSCT) or solid organ transplantation (SOT). For more than 15 years voriconazole, a drug of the triazole class, has been the recommended treatment for this life-threatening infection after a pivotal randomized trial showed an improved survival with voriconazole compared with amphotericin B deoxycholate. However, also with voriconazole the overall 6-week mortality is still unacceptably high at 25-30% (Herbrecht et al., 2002¹). Therefore, a randomized controlled trial assed the efficacy of voriconazole with or without anidulafungin for the treatment of IA in haematology patients to prove that combination therapy can improve outcome. Among the 277 patients with IA in this study, the 6-week mortality with combination therapy was 30% lower (19.3%) than with monotherapy (27.5%), p=0.087. In a post-hoc analysis of the 222 patients with radiographic abnormalities and a positive galactomannan antigen test, a statistically significant difference in mortality was observed (p=0.037). Though, this study did not result in conclusive evidence in favor of combination therapy, it is a credible study which adds to the already existing in vitro and animal studies in support of echinocandin triazole combination therapy for IA and thus paves the way for a second larger and pragmatic clinical trial. Another important and new consideration about the management of IA is the upcoming of infections with triazole-resistant A.fumigatus. This is increasingly becoming a worldwide problem and leads to longer hospital stay, higher costs and is associated with a very high mortality. It is very likely that the exces-

sive use of antifungals of the triazole class in agriculture has formed the basis of this problem. Since 2018 the Dutch Working Party on Antibiotic therapy (SWAB) guideline on the management of invasive fungal infections therefore recommends upfront combination therapy (azole plus echinocandins or liposomal-amfotericine B) until resistance can be excluded as one of the treatment options for IA.

Given the evidence in favor of voriconazole-echinocandin combination therapy as well as the increasing incidence of voriconazole-resistant *A. fumigatus* in Belgium and the Netherlands, a large clinical study on the value of combination therapy is urgently needed.

Objectives

Primary objective

1. Evaluate if the survival in patients with a triazole susceptible IA can be improved when the initial therapy consists of triazole and echinocandin combination therapy instead of triazole monotherapy. This objective is captured in the primary endpoint as well as secondary endpoints 1 to 6)

Secondary objectives

- 1. Evaluate if a triazole/echinocandin combination therapy improves the overall quality of life and if it is a cost-effective intervention (these objectives are captured in secondary endpoint 11 and 12)
- Evaluate the outcome of patients in which a triazole-resistant A. fumigatus is detected in relation to the initial antifungal therapy they had received (i.e. triazole monotherapy or combination therapy). This objective translates into secondary endpoint 7 an 8.
- 3. Evaluate the outcome of patients in which resistance testing is unsuccessful in function of the antifungal therapy they received. This translates into secondary endpoint 10.
- 4. Evaluate if the baseline serum galactomannan value and the serum galactomannan kinetics are predictive of overall 6-week survival. This translates into secondary endpoint 3 and 9.

Study design and intervention: The study is designed as a large pragmatic clinical trial to facilitate enrolment as much as possible. In particular, we want to leave the choice of the triazole (voriconazole or isavuconazole or posaconazole IV or oral) to the treating physician. This will not only lead to less patients being excluded but also allow the clinician to switch from one drug to another (within the same class) in case of treatment limiting toxicity. With the unbiased endpoint of overall survival, we consider a pragmatic approach that allows for easy recruitment of a sufficient number of patients

more important than the use of one specific drug within a class or the use of a placebo. Combination therapy will be discontinued after 28 days in all patients in which triazole susceptibility has been documented but when a treatment response is observed before day 28, the echinocandin can be discontinued as from day 7.

Study population

Immunocompromised patients who fulfill the EORTC/MSG host factor and mycological criteria of invasive aspergillosis ICU patients with influenza who fulfill a definition of IA specific for this population

Primary endpoint

Primary endpoint

Overall survival 42 days after the start of antifungal therapy in the MITT population

Secondary endpoints

- Overall aspergillus attributable mortality 12 weeks after the start of antifungal therapy.
- 2. Overall survival 12 weeks after the start of antifungal therapy in the MITT population
- 3. Overall survival 6 weeks after the start of therapy in the subgroup of patients in the MITT population with a positive serum galactomannan test at baseline.
- 4. Overall survival 6 weeks after the start of therapy in the subgroup of non-ICU patients who fulfill the EORTC/MSG probable or proven definition (MITT population).
- 5. Overall survival 6 weeks after the start of therapy in the subgroup of non-ICU patients with an underlying haematological disease (MITT population)
- 6. Overall survival 6 weeks after the start of therapy in the subgroup of non-ICU patients without an underlying haematological disease (MITT population)
- 7. Overall survival 6 weeks after the start of therapy in patients that started with triazole monotherapy and in which triazole resistance is detected during follow-up (MITT population)
- 8. Overall survival 6 weeks after the start of therapy in patients that started with triazole-anidulafungin combination therapy and in which triazole resistance is detected during follow-up (MITT population)
- 9. In the subgroup of patients with a positive serum galactomannan; Kinetics of serum galactomannan levels with combination versus monotherapy
- 10. Outcome of patients in which resistance testing was unsuccessful
- 11. Time to hospital discharge (in the MITT subgroup of patients admitted to the hospital at baseline)
- 12. Cost-effectivity of azole-anidulafungin combination therapy

Nature and extent of the burden and risks associated with participation, benefit and group relatedness: The safety of this combination therapy has previously been demonstrated in a large randomization clinical trial (Marr et al., 2015).2 As a result of the underlying disease as well as the chemotherapy, serious adverse events are very frequently observed in this patient population (e.g. bleeding, life threatening infections, death due to progression of the underlying disease). The study will comprise of 4 study visits and as most patients will be hospitalized at the start of therapy few of these will be additional hospital visits on top of the standard of care.

This video presentation describes the study in more detail as well https://www.youtube.com/watch?v=Kng58Zar4hY

1. INTRODUCTION AND RATIONALE

Invasive aspergillosis (IA) is a common complication during remission inducing chemotherapy for acute leukemia as well as in those who have undergone allogeneic hematopoietic stem cell transplantation (HSCT) or solid organ transplantation (SOT). For more than 15 years voriconazole, a drug of the triazole class, has been the recommended treatment for this life-threatening infection after a pivotal randomized trial showed an improved survival with voriconazole compared with amphotericin B deoxycholate. However, also with voriconazole the overall 6-week mortality is still unacceptably high at 25-30% (Herbrecht et al., 2002¹). Voriconazole blocks the synthesis of ergosterol, a part of the fungal membrane, while antifungals from the echinocandin class block the synthesis of B-(1,3)-D glucan, a component of the cell wall. Both drugs may therefore work synergistically as suggested by in vitro studies, neutropenic animal models of IA and case series (Philip et al., 2005³; Petraitis et al., 2003⁴). This synergistic effect was the hypothesis of a randomized trial that assessed the efficacy of voriconazole with or without anidulafungin for the treatment of IA in haematology patients (Marr et al., 2012²). Among the 277 patients with IA in this study, the 6-week mortality with combination therapy was 30% lower (19.3%) than with monotherapy (27.5%), p=0.087. In a post-hoc analysis of the 222 patients with radiographic abnormalities and a positive galactomannan antigen test, a statistically significant difference in mortality was observed (p=0.037). These results were clearly promising and although we agree that in real-life in haematology patients a diagnosis of IA is indeed very often based on the combination of a positive galactomannan and pulmonary abnormalities, formal conclusions on the value of combination therapy cannot be based on a post-hoc analysis from a single clinical trial. This is the reason why, despite the 30% relative reduction in mortality that was observed, combination therapy has not been included as preferred

first choice therapy for all patients with IA in the 2017 ESCMID guideline nor in the 2017 Dutch SWAB guideline. Therefore, a second clinical trial is needed to confirm this finding.

Another important reason to study upfront combination therapy for patients with IA in the Netherlands and Belgium is the increasing incidence of triazole-resistant A. fumigatus. Indeed, from a global perspective the highest prevalence of triazole resistance has been documented in the Netherlands. It increased from 0% before the year 2000 to 5.3% in 2009, and further increased to 15% in 2017. Unfortunately, more recently triazole resistance was observed in 5% of IA cases in Belgium as well and in 2017 researchers from the Erasme hospital in Brussels even reported a prevalence of 13% (Vermeulen et al., 2015⁵; Montesinos et al., 2017⁶). It has also clearly been demonstrated that the overall mortality becomes very high (50-88%) when patients infected with a triazoleresistant A. fumigatus initially receive inappropriate voriconazole therapy and therapy is only changed at a time when it has become clinically obvious that the IA is progressing (Lestrade et al., 2018⁷, van der Linden et al., 2015⁸; Chong et al., 2015⁹). These important observations recently led to a change in the treatment recommendations of the 2017 Dutch SWAB guideline on fungal infections. In the absence of any evidence from prospective studies on the treatment of IA in regions with a high prevalence of azole resistance, this guideline recommends 2 possible strategies. The first is upfront combination therapy (triazole combined with an echinocandin or liposomal amphotericin B) until resistance can be excluded. The second option, which should only be considered in non-critically ill patients and in centers that are able to perform real-time PCR as well as cultured based resistance testing on BAL samples, is to start with voriconazole monotherapy while waiting for the resistance test (Kullberg et al., 2018¹⁰). Unfortunately, resistance testing will not lead to an interpretable result in approximately 35% of the patients with IA. Indeed, fungal cultures remain negative in the majority of the patients with IA and PCR testing for CYP51 resistance associated mutations is not always successful either. For this subgroup of patients, the SWAB guideline recommends switching from triazole monotherapy to combination therapy as soon as it becomes clear that no resistance result will become available. The latter recommendation has been criticized when it relates to patients that are not very sick and have an infection that is limited to the lungs and that is not widespread. Indeed, some clinicians argue that close monitoring for treatment progression is a valid option as well because the poor outcome of azole resistant IA has not (yet) been convincingly demonstrated for culture negative cases.

The goals of this study are therefore 3-fold.

First, the main study and the primary endpoint will evaluate if the overall mortality can be decreased with initial azole-echinocandin combination therapy compared with triazole monotherapy in patients with IA and documented *voriconazole susceptibility*.

Second, the study design described below will also allow to study several other subpopulations; Indeed, the outcome of the following subgroups will be evaluated as well; a. Patients starting azole monotherapy but who switch to directed therapy when it has become clear that the infection is caused by an azole resistant A. fumigatus. b. patients in which eventually no resistance data become available in relation to the treatment they received.

Third, we want to evaluate what the outcome is of patients that turn out to be infected with a triazole resistant A. fumigatus who started with a triazole-echinocandin combination therapy.

Please note that a 20-minute presentation with illustrated slides has been put together in order to explain the background and the design of the study. This presentation is available via this URL: https://www.youtube.com/watch?v=Knq58Zar4hY and may help to understand the design and logistics of the study as an introduction to the full protocol

2. OBJECTIVES

Primary objective

1. Evaluate if the survival in patients with a triazole susceptible IA can be improved when the initial therapy consists of triazole and echinocandin combination therapy instead of triazole monotherapy. This objective is captured in the primary endpoint as well as secondary endpoints 1 to 6)

Secondary objectives

- 1. Evaluate if a triazole/echinocandin combination therapy improves the overall quality of life and if it is a cost-effective intervention (these objectives are captured in secondary endpoint 11 and 12)
- 2. Evaluate the outcome of patients in which a triazole-resistant A. fumigatus is detected in relation to the initial antifungal therapy they had received (i.e. triazole monotherapy or combination therapy). This objective translates into secondary endpoint 7 an 8.
- 3. Evaluate the outcome of patients in which resistance testing is unsuccessful in function of the antifungal therapy they received. This translates into secondary endpoint
- 4. Evaluate if the baseline serum galactomannan value and the serum galactomannan kinetics are predictive of overall 6-week survival. This translates into secondary endpoint 3 and 9.

3. STUDY DESIGN

A non-blinded phase 3 multicenter randomized pragmatic clinical trial.

Intervention: Add anidulafungin IV to the standard of care therapy that consists of a triazole (voriconazole or isavuconazole or posaconazole).

In both the intervention and control group, the triazole will be given for at least 6 weeks. In the intervention group the echinocandin will be discontinued after 28 days but when a treatment response is observed and the patients can be discharged from the hospital, the echinocandin can be discontinued from day 7 onwards according to the choice of the treating physician. Figure 1 illustrates the study design and the patient flow in the study. The youtube presentation https://www.youtube.com/watch?v=Knq58Zar4hY also clearly explains this flowdiagram.

4. STUDY POPULATION

4.1. Population (base)

The study population will consist of patients age 18 or older that fulfill the host-factor definition of the EORTC/MSG¹¹ in combination with any pulmonary infiltrate and a positive fungal culture from a bronchoalveolar lavage or positive serum (optical density ≥ 0.5) or BAL galactomannan (optical density ≥ 1.0). This not only includes patients with proven or probable IA but also patients with a pulmonary infiltrate that does not comply with the EORTC radiological criteria (halo, nodule, cavitary lesion). We consider the inclusion of this latter patient population important as well because not only the mortality of these patients is comparable to patients with an EORTC/MSG probable IA but clinicians also uniformly treat these patients in the same way as they treat patients with probable IA (Nucci et al., 2010^{12}).

The host-factor definition of the EORTC/MSG implies that not only patients with an underlying haematological disease can be included but any patients that is sufficiently immunocompromised to fulfil the host-factor definition. Furthermore, ICU patients with a predicted mortality not exceeding 50% and admitted with influenza and respiratory insufficiency can be included as well as this has recently been described as an important risk factor for IA by Schauwylieghe et al¹³.

4.2. Inclusion criteria

Patients should fulfill the following inclusion criteria:

1. 18 years or older

- 2. Have started or will start voriconazole or isavuconazole (or posaconazole if voriconazole or isavuconazole cannot be given as per treating physician's decision) as antifungal therapy on the baseline visit.
- 3. For all patients: presence of one of the EORTC/MSG host factors as defined in appendix 1 or being admitted to the ICU with influenza
- 4. For non-ICU patients or ICU patients without influenza: Meet the EORTC/MSG clinical criterium (appendix 1)
- 5. For non-ICU patients or ICU patients without influenza: Meet the mycological criterium (appendix 1) or fulfil inclusion criterium 7
- 6. For ICU patients with influenza we consider an isolated positive sputum culture for Aspergillus spp. insufficient as a mycological criterium. Therefore, in these patients only one of the following mycological criteria are acceptable; Serum galactomannan □0.5, BAL galactomannan □1.0 or *Aspergillus* spp. cultured in BAL fluid.
- 7. Please note that patients with AML receiving chemotherapy or patients with ALL receiving or having received corticosteroid therapy within the last 4 weeks in the context of their pre-phase, induction, consolidation, intensification or interphase treatment as well as patients receiving systemic immunosuppressive therapy for GVHD can be included before the mycological criterium is fulfilled on condition that they fulfill the EORTC/MSG lung CT radiology criteria (halo sign, well-described nodule, cavity as described in appendix 1) at the time of inclusion and as long as the mycological test results are expected to become available within 96 and no later than 7 days after inclusion. If these test results turn out to be negative, the patient will be withdrawn from the study and further treatment is at physician's discretion.

4.3. Exclusion criteria

- 1. Known history of allergy, hypersensitivity or serious reaction to azole or echinocandin antifungals;
- 2. Patients with chronic invasive aspergillosis or a chronic non-invasive aspergillus infection (e.g. aspergilloma) defined as the clinical or radiological sign of infection being present for >28 days.
- 3. Receipt of itraconazole, voriconazole, posaconazole or isavuconazole as prophylaxis for at least 7 days in the 14 days preceding the date of the first radiological signs of the Aspergillus infection. Patients in which the most recent serum level of the triazole given as prophylaxis was subtherapeutic can be included (*).
- 4. Receipt of echinocandin prophylaxis for >96 hours in the preceding 7 days
- 5. Receipt of systemic antifungal treatment with an echinocandin or an azole for the current episode of invasive aspergillosis for a duration of > 96 hours.

- 6. For patients in the Netherlands only: Diagnostic testing to exclude azole resistance will not be possible (sputum cultures are negative and BAL sampling will not be performed)
- 7. ICU patients only: Patients with a sequential organ failure assessment (SOFA) score >11 at the time of screening for the study are excluded. If randomization is done >24 hours after screening the calculation should be repeated before the patient can be randomized (appendix 3)
- 8. ICU patients only: Patients in which weaning from the ventilator or ECMO system is deemed unlikely due to irreversible lung damage
- Patients with any condition which, in the opinion of the investigator, could affect
 patient safety, preclude evaluation of response (e.g. because survival beyond 6
 weeks is unlikely due to the underlying disease status)
- 10. Patient previously included in this study
- (*) Subtherapeutic levels are defined as itraconazole (parent compound only) <0.5 mg/L or posaconazole <0.7mg/L or voriconazole <1.0mg/L or isavuconazole <1.0mg/L

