5. TREATMENT OF SUBJECTS

5.1. Investigational product/treatment

Anidulafungin

Detailed information on anidulafungin, the investigational product used in this study can be found in the SPC. A short summary is given here. The information currently available on combination therapy with a triazole and an echinocandin for the treatment of IA is described below (6.2).

Mechanism of action

Anidulafungin is a semi-synthetic echinocandin, a lipopeptide synthesised from a fermentation product of Aspergillus nidulans. Anidulafungin selectively inhibits 1,3-8-D glucan synthase, an enzyme present in fungal, but not mammalian cells. This results in inhibition of the formation of 1,3-beta-D-glucan, an essential component of the fungal cell wall. Anidulafungin has shown fungicidal activity against Candida species and activity against regions of active cell growth of the hyphae of Aspergillus fumigatus.

Chemical Name

Anidulafungin has the chemical name 1-[(4R,5R)-4,5- Dihydroxy-N2- [[4"-(pentyloxy) [1,1':4',1"-terphenyl]- 4- yl]carbonyl]- Lornithine]echinocandin B.

Name of medicinal product

ECALTA 100 mg powder for concentrate for solution for infusion

Method of administration

For intravenous use only.

ECALTA should be reconstituted with water for injections to a concentration of 3.33 mg/mL and subsequently diluted to a concentration of 0.77 mg/mL.

Dosage & duration

Adult patients receive a loading dose on day-1 of 200mg IV, followed by 100 mg daily thereafter.

Anidulafungin will be given for at least 7 days but no longer than 28 days. Please note that this refers to the MITT primary endpoint population. In patients in which triazole resistance is demonstrated or in which the results of the resistance test are inconclusive, the treatment duration of combination therapy can be much longer. These patients are not included in the MITT primary endpoint population.

Intervention

Treatment with a triazole (voriconazole or isavuconazole or posaconazole) + anidulafungin IV. The triazole is administered for at least 6 weeks while anidulafungin is given for at least 7 and a maximum of 28 days.

Comparator

Treatment with a triazole (voriconazole or isavuconazole or posaconazole) for at least 6 weeks.

In both groups, the route of administration is according to the choice of the treating physician as well as the decision to perform or not perform therapeutic drug monitoring of the triazole drug.

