9.3. Multiplicity

There is only 1 primary endpoint and no interim analysis for efficacy will be performed. Therefore, the primary endpoint will be tested at the α =0.05 level (two-sided test).

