9.5. Sample size calculation

In the pivotal trial on voriconazole and anidulafungin combination therapy the mortality in the voriconazole control group was 28% 6 weeks after the start of therapy. This study only included patients with an underlying haematological disease. Furthermore, in a large pragmatic trial with fewer exclusion criteria and in which a small number of ICU patients will be included as well, we expect a somewhat higher mortality of 35%, We consider a 33% lower overall mortality with combination therapy (=from 35% to 23,33%) compared to monotherapy of clinical importance. This leads to a sample size of 237 evaluable patients per group (=included in the mITT population as defined above) to show superiority of combination therapy compared with monotherapy with an alfa of 0.05 and a power of 80%. Follow-up for the primary endpoint is 6 weeks after the start of antifungal therapy.

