11.4. Benefits and risks assessment

Anidulafungin has been registered and used in the Netherlands for the treatment of invasive candida infections for >10 years and is considered a very safe drug. Also, the safety of the combination of anidulafungin and voriconazole that the patients in the intervention group will receive has previously been demonstrated in a large randomization clinical trial.² The risks are therefore considered very low.

If the improved mortality with combination therapy that was observed in the study by Marr K et al. is confirmed in our study, the patients in the study as well as future patients may potentially benefit from this combination treatment.

Hepatic metabolism of anidulafungin has not been observed and anidulafungin is not a clinically relevant substrate, inducer, or inhibitor of cytochrome P450 (CYP450) isoenzymes. It is therefore very unlikely that anidulafungin will have significant drug-drug interactions with concomitant medication taken by the patient.

As a result of the underlying disease as well as the chemotherapy, serious adverse events are very frequently observed in this patient population (e.g. bleeding, life threatening infections, death due to progression of the underlying disease). The study will comprise of 4 study visits and as most patients will be hospitalized at the start of therapy few of these will be additional hospital visits on top of the standard of care.

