APPENDIX 2: PATIENT VISIT SCHEDULE

	Screening	Baseline (D1)	D2-6	D3	D5	D7	D8-D28	D14	D28	D42	D84	D168	D8-28
Eligibility check ^(#)	Х	X ^(#)											
Informed consent		Х											
Study drug administration ^(^)		Х	Х			Х	(x)						Х
Medical history		Х											
Serum sampling ^(*)		Х		Х	х	Х		Х	Х				
Patiënt details		Х											
Register use of any antifungals		Х						Х	Х	Х	Х	Х	
Register use of TPV or EN after baseline visit										Х		Х	
Register use of any blood products administered after baseline visit										Х		Х	
Register hospital and ICU days from baseline to week 24										Х		Х	
Quality of life questionnaire		Х								х	х	Х	
Loss of income questionnaire		Х									х	Х	
Neutropenic status		Х				Х		х	х	х	х		
Survival status						Х		Х	Х	Х	Х	Х	

Please note that few exceptions notwithstanding, screening and baseline visit will be done on the same day.

Gray columns indicate the days that a hospital visit is required: Although the large majority of the patients will be in the hospital during the first week of therapy some patients will be outpatients. Patients who are outpatients and are included in the study are required to visit the outpatient clinic for study drug administration up until day 7.

Please note that, except for the screening and baseline visit, none of the other visits require an additional patient visit to the hospital as all these data can be collected from the patient files and by contacting the patient or the general practitioner or relatives of the patient.

(°) For the patients randomized in the combination therapy group. The minimum duration of study drug treatment is 7 days. After day 7 and up until day 28 the investigator decides if the treatment needs to be continued for a maximum of 28 days.

(#) For ICU patients the SOFA score should be recalculated if >24hrs pass between screening and baseline and patient excluded if SOFA has increased to >11 points.

(*) This should only be done if the patient is still in the hospital or visiting the outpatient clinic at these study dates. Please note that the day 14 and day 28 sampling can be done between day 11 and 17 and day 25 and 31 respectively (so day 14±3days and day 29±3days). The standard operating procedure regarding serum sampling and storage of serum by the lab is described in appendix 6 in more detail.

TPV= total parenteral nutrition. EN= enteral nutrition.

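### The echinocandin exclusions are tied to indication, so a patient already committed to an echinocandin for another infection can be randomised to triazole monotherapy, which dilutes the contrast

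*Protocol*

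**What the plan says.** Two exclusions in protocol section 4.3 deal with echinocandins. Exclusion 4 reads "Receipt of echinocandin prophylaxis for >96 hours in the preceding 7 days". Exclusion 5 reads "Receipt of systemic antifungal treatment with an echinocandin or an azole for the current episode of invasive aspergillosis", with a limit of 96 hours. The first depends on the drug being prophylaxis, the second on its being treatment of the present aspergillosis.

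Section 11.4 describes anidulafungin as "registered and used in the Netherlands for the treatment of invasive candida infections for >10 years", so the protocol itself names a reason other than aspergillosis for giving this class.

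Section 5.1 defines the comparator as "Treatment with a triazole (voriconazole or isavuconazole or posaconazole) for at least 6 weeks", and section 7.2 names the two arms monotherapy and combination therapy. Sections 5.2 (co-intervention) and 5.4 (escape medication) are marked not applicable. Section 7.1.4 removes randomised patients from the MITT for lack of timely positive mycology, for documented voriconazole resistance and, in the Netherlands, for unsuccessful resistance testing. Echinocandin use outside the allocation is not a ground for removal. Appendix 2 has a row "Register use of any antifungals" at baseline and at days 14, 28, 42, 84 and 168.

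**The concern.** The trial asks whether adding an echinocandin to a triazole lowers six-week mortality. A patient who is on an echinocandin for another infection at randomisation, and will stay on it, cannot help to answer that. Allocation may change which echinocandin is given and for how long, but not whether one is given.

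The exclusions treat such patients unevenly. Five days of echinocandin prophylaxis in the week before entry keeps a patient out. A longer treatment course for another infection, still running at entry, does not. The sponsor evidently meant to limit non-study echinocandin exposure, and the wording misses one route.

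At stake are power and the reading of a null result. A diluted difference would also enter the conditional power calculation at the futility look in section 7.7. The protocol does consider control patients moving to combination therapy, but section 5.3 addresses this only where the motive is fear of resistance.

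**Working it through.** **Does any provision close the gap?** Take a patient with aspergillosis who has had ten days of an echinocandin for a Candida infection and will continue it.

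- Exclusion 4: not met, because the drug is treatment and not prophylaxis.
- Exclusion 5: not met, because the drug was not given for the current aspergillosis.
- Exclusion 9 (investigator's opinion): could be used, but it is discretionary, its example is unlikely survival, and it does not mention echinocandins.
- MITT definition (7.1.4): none of the grounds for removal applies.

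The patient is eligible and, if allocated to control, is analysed as monotherapy.

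**Inputs for the size of the effect.**

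- Control mortality: section 9.5 says "we expect a somewhat higher mortality of 35" per cent.
- Combination mortality: 23.33% (section 9.5).
- Sample size: 237 evaluable patients per group (section 9.5), allocated 1:1 (section 7.2).
- Error rates: section 9.5 sizes the trial "with an alfa of 0.05 and a power of 80" per cent, and section 9.3 says "the primary endpoint will be tested at the α =0.05 level (two-sided test".
- c, the share of controls who receive an echinocandin with full combination benefit: not in the protocol, so assumed.

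**Reproducing the plan's figure.** With p1 = 0.35, p2 = 0.2333 and mean p = 0.29165, the normal approximation with pooled null variance is

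n = [1.96 × √(2p(1−p)) + 0.8416 × √(p1(1−p1) + p2(1−p2))]² / (p1−p2)²

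= [1.2598 + 0.8416 × 0.6375]² / 0.1167² = 236.9, so 237 per group. The stated sample size is correct for its inputs.

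**Dilution.** Control mortality becomes p1(c) = 0.35(1−c) + 0.2333c, so the expected difference is (1−c) × 11.67 percentage points. Power at n = 237 is

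Φ{[(p1(c)−p2)√n − 1.96√(2p(1−p))] / √(p1(c)(1−p1(c)) + p2(1−p2))}

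with p recalculated for each c. At c = 5%: p1 = 0.3442 and the difference is 0.1109, which gives Φ[(1.7067 − 1.2561)/0.6361] = Φ(0.708) = 0.761.

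| c (assumed) | Controls affected, of 237 | Control mortality | Difference (points) | Power at 237 | n per group for 80% |
|---|---|---|---|---|---|
| 0 | 0 | 35.0% | 11.7 | 80.0% | 237 |
| 2% | about 5 | 34.8% | 11.4 | 78.5% | 247 |
| 5% | about 12 | 34.4% | 11.1 | 76.1% | 262 |
| 10% | about 24 | 33.8% | 10.5 | 71.7% | 290 |

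Taking the combination rate as exactly two thirds of 35% changes the 5% row to 76.0% and the undiluted n to 238; the other powers are unchanged to one decimal.

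**What the table assumes.** Each affected control is given the full combination-arm mortality and is otherwise of average risk. The study course is a loading dose followed by at least 7 and up to 28 days (section 5.1), and a course for another infection need not match it. If such patients gained only half the effect, c = 10% would act like c = 5% in the table. For each c, therefore, the loss shown is an upper bound.

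**The case against.** The case on the other side has four parts.

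1. *The control arm is labelled monotherapy.* A non-study echinocandin there departs from the allocated treatment, and section 12.1 requires deviations and their reasons to be recorded. Marking sections 5.2 and 5.4 not applicable is not permission to add one. This largely stands. A reader might infer that the protocol freely allows echinocandin in controls throughout follow-up, and the text does not support that. The label and the recording duty do not, however, stop the patient being randomised or counted in the MITT. Figure 1, which section 12.1 cites on changes of therapy, is not visible in the copy reviewed, so a restriction shown only there cannot be ruled out.

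2. *The group is narrow and its size unknown.* This stands. Section 11.4 states a registered use and does not say how often the two infections coincide. At c = 2% the loss is 1.5 points, and the document offers no basis for 5% or 10%.

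3. *An entry criterion cannot prevent an echinocandin being started later for a new infection.* This stands, and that situation is outside the point. Such use arises after randomisation, can occur in either arm, and belongs in the analysis by randomised arm.

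4. *Broad entry is a declared pragmatic choice.* This is true of the design in general, and section 7.1.3 gives reasons for each widening. None of those reasons concerns patients for whom allocation cannot decide whether they receive an echinocandin, and enrolling them does not serve the pragmatic question.

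**Conclusion.** The gap is real and limited. As section 4.3 is written, a patient already committed at randomisation to an echinocandin for an infection other than the current aspergillosis can enter, be allocated to monotherapy and be analysed as such. The effect is towards no difference. Type I error is not affected, and the calculation of 237 per group is right for its stated inputs.

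The size cannot be fixed from the protocol. Under the stated assumptions the power loss is at most 1.5 points at c = 2%, about 4 points at 5% and about 8 points at 10%, and smaller with short or partial courses. It would be wrong to infer that the trial is underpowered, or that controls will commonly receive the tested combination: the document supplies no frequency for either reading. Nor does the point extend to patients whose earlier echinocandin would stop at entry. The case for acting is that the omission is specific and cheap to close, and concerns the one contrast on which the trial is powered.

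**What to change.** Reconcile exclusions 4 and 5 in section 4.3 with the monotherapy comparator in sections 5.1 and 7.2, so that eligibility also addresses patients in whom an echinocandin for an infection other than the current aspergillosis will be given after randomisation whatever the allocation. The clinical wording, including how that commitment is judged at entry, is for the sponsor. The line should not reach patients whose earlier course ends at entry.

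Echinocandin started later for a new infection needs no eligibility rule. Such patients stay in their randomised arm, and the share of controls who received any echinocandin can be tabulated from the antifungal data already scheduled in Appendix 2, so that a reader can judge the actual dilution.

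The cost is one eligibility line and the loss of a few patients, whose allocation would not have changed whether they received an echinocandin. No new data collection and no change to the sample size are needed.
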